1.6 Risk/Benefits

Overall risks of this protocol are minimal. All risks will be spelled out in simple language on the consent form. All subjects must give informed consent prior to research participation.

The surveys and interviews are non-invasive and minimal risk. There is a possibility that some questions might be embarrassing or uncomfortable. Patients will be reminded that they have the right to refuse to answer any questions they wish.

With research participation, there is always a risk of data and privacy breach. All measures will be taken to protect the confidentiality of patients involved in the study by assigning a study identifier to each subject. Study data will be stored on a secure, web-based application called REDCap, and/or on a Department of Neurology computer or server managed by the Information Services department at Dartmouth-Hitchcock Medical Center. Paper records will be kept in Department of Neurology research offices, which are locked when not in use, and in long term storage managed by the Records Management/Health Information Services department. Ten years after completion of the study, all identifying information will be eliminated.

Pupillometry, vibrotactile detection thresholds, and neurocognitive/neuropsychiatric tests are non-invasive and carry minimal risk. Cognitive questionnaires could conceivably be frustrating to the patient, or questionnaires may ask about troubling symptoms such as depression. Patients will be reminded they can withdraw at any time or choose not to answer certain questions they find bothersome.

Venipuncture will be required to obtain blood samples as part of our protocol. Venipuncture is minimal risk but carries with it the risk of discomfort, bruising, bleeding, swelling, infection, and pain. Standard precautions will be followed during intravenous catheter placement and blood draws by trained personnel accustomed to these procedures as part of tilt-table testing.

Both autonomic testing and tilt-table testing are minimally invasive but can precipitate hypotension, bradycardia or tachycardia, palpitations, anxiety, presyncope, or frank syncope with

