6.1 Description of NeuroOptics® PLR-3000

All subjects will undergo pupillometric evaluation with the NeuroOptics® PLR-3000. The PLR-3000 system automatically measures monocular resting pupillary size using infrared light in a dark room, and then uses a brief light flash to measure minimum post-contraction pupillary size, contraction velocity, contraction latency, redilation velocity, and time of pupillary redilation. Pupillometric methods have been described previously⁷⁰⁻⁷² and will be modified for use with the NeuroOptics system. Testing will be done twice in each eye. Binocular pupillometric data collection will take less than 5 minutes to obtain. Bilateral results will be averaged for final

comparison. If there is a unilateral preexisting condition (e.g. untreated cataract), pupillometric evaluation will be limited to the unimpaired side with no averaging. We will measure these parameters at baseline with the patient at rest and room lights as dim as possible, then again with lights on. Pupillometry will be performed in the same room to maintain minimal variation in luminance. We will repeat these studies after yohimbine administration at the time of the second HUT.

7 Study Procedures

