7.1 Schedule of Assessments

Event/Assessment	Visit 1			Visit 2 (occurs no more than 30 days after V1)		Follow-Up Phone Call (24-72 hours after Visit 2)
Informed consent	X					
Inclusion/Exclusion criteria	X					
Demographics	X					
Medical history	X					
History and current use of alcohol	X					
Current and prior smoking status	X					
UPDRS, Hoehn & Yahr staging	X					
Orthostatic vital signs (OVS)	X Baseline: holding L-dopa	X 30 min after L-dopa administration	X 1 hour after L-dopa administration	X pre yohimbine administration	X post yohimbine administration	
Serum Pregnancy Test (WOCBPO) ⁱ	X					

Event/Assessment	Visit 1			Visit 2		Follow-Up Phone Call (12 to 72 hours after Visit 2)
Urine Pregnancy Test (WOCBPO)				X		
Concomitant medications	X			X		X
Adverse Events	X			X		X
SCOPA-AUT	X					
HR and BP response to DB and Valsalva	X					
Vibrotactile detection thresholds	X					
Neurocognitive testing	X					
Neuropsychiatric assessment	X					
Neuropsychiatric assessment (Informant)	X					
Dynamic pupillometry	X (holding levodopa)		X (1 hour after levodopa administration)	X (pre yohimbine administration)	X (post yohimbine administration)	
C-SSRS Baseline Version	X					

Event/Assessment	Visit 1		Visit 2		Follow-Up Phone Call (12 to 72 hours after Visit 2)
CSSRS- Since Last Visit Version			X		
IV placement			X		
HUT			X (pre yohimbine administration)	X (post yohimbine administration)	
Visual analogue scales measuring anxiety, mood, fatigue			X pre -yohimbine administration	X post- yohimbine administration	
Serum AVP ⁱⁱ and NE ⁱⁱⁱ			X Pre Yohimbine administration	X Post Yohimbine administration	
Safety Labs (CBC, CMP) ^{iv}	X				

ⁱ Women of Child Bearing Potential Only

ⁱⁱ AVP will be draw after approximately 30 minutes supine and again at approximately 15 minutes upright tilt to 60 degrees.

ⁱⁱⁱ NE drawn after approx.30 minutes supine and again at approximately 5 minutes after upright tilt to 60 degrees

^{iv} If labs have been drawn within past 6 months and are WNL or with abnormalities that are NCS; those can be utilized for inclusion

7.2 Visit 1

- Informed consent
- Confirmation of Inclusion/Exclusion
- Demographic collection
- Medical History data collection
- Vital Signs
- Serum Pregnancy Test (women of childbearing potential only)
- Serum Safety Labs for CBC, CMP (if not completed in past 6 months)
- Orthostatic Vital Signs
 - Baseline, (holding AM dopamine)
 - Approx 30 minutes after dopamine administration

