- Activation-Deactivation Checklist to assess arousal (AD-ACL) ⁹¹

Patients will also complete a visual analogue scale before and after yohimbine to assess for acute changes in symptoms such as anxiety, fatigue, and concentration/attention [VAS; score ranging from 0% (no symptoms) to 100% (most severe symptom possible)]. ⁹⁵

An informant (when available) will complete informant report versions of the BRIEF-A, AES, as well as the Neuropsychiatric Inventory Questionnaire (NPI-Q). ⁹²

The total time for neurocognitive and neuropsychiatric testing will be approximately 1.5 hours.

Peripheral nerve testing:

This following peripheral nerve testing will performed by trained autonomic technicians and interpreted by the PI or a sub-I.

- HR and continuous BP variability monitoring with deep breathing and Valsalva.
- Patients will answer a validated survey to quantify their autonomic symptoms (the SCOPA-AUT).⁹³
- Measurement of vibrotactile detection thresholds.⁹⁴
- Dynamic pupillometry testing prior to subjects taking their levodopa-, and then again approximately 60 minutes after ingestion. See section 6.1 for pupillometry protocol.

7.3 Visit 2

HUT will be done first thing in the morning, since subjects will be holding their levodopa and other medications that could interfere with autonomic testing. Subjects will fast and abstain from coffee the morning of testing but will be encouraged to hydrate exuberantly.

[figure not shown]
Prior to beginning the HUT, the following will occur:

- Collection of adverse events since consent was signed /changes in medical history
- Collection of changes in concomitant medication will be collected.
- A C-SSRS, (Since Last Visit), will be also be performed.
- Urine pregnancy test will be performed prior to starting the HUT, (if a women is of childbearing potential,).

The following procedures will be performed as part of the HUT and measured per HUT protocol^{6, 22}, while under the supervision of a cardiac electrophysiologist, cardiology nurse and study coordinator.

- IV will be placed per standard HUT procedure.
- After approximately 30 minutes of supine rest:
 - Serum AVP and NE levels draw for baseline level
 - VAS scale completion for baseline/resting anxiety, fatigue and mood, ([VAS; score ranging from 0% (no symptoms) to 100% (most severe symptom possible)]⁹⁵).
- Pupillometric evaluations (see Figure 2).
- Tilt table to approximately 60 degrees for approximately 15 minutes; return to supine
- Yohimbine administration

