- VAS scale completion for baseline/resting anxiety, fatigue and mood, ([VAS; score ranging from 0% (no symptoms) to 100% (most severe symptom possible)]⁹⁵).
- Patients will then be tilted to 60 degrees for a second time and remain in that position for approximately 15 minutes.
- NE will be drawn approximately 5 minutes after being tilted up to 60 degrees.
- AVP will be drawn approximately 15 minutes after being tilted up to 60 degrees.

Figure 2. Timeline of Visit 2

The total time for Visit 2 will be approximately **4-6 hours**, pending observation time post yohimbine administration (see Figure 2 above).

A cardiac electrophysiology sub-investigator, who will be trained in the protocol and drug effects, will monitor the tilt test, as well as halt the test in the unlikely case of dangerous syncope, arrhythmia, or intolerable symptoms. Yohimbine may even improve orthostasis.^{65, 66}

[name], or a designated sub-investigator, will be available via pager during all scheduled visit 2 activities. In the event of any adverse events during yohimbine administration and HUT, he will be available to assess and document any adverse effects clinically and identify a plan for clinical treatment, should any be necessary. Any adverse events occurring during yohimbine administration and HUT involving autonomic nervous system function and vital signs will be monitored for at least 3 hours post event to assure stable vital signs/condition.

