8.2 Statistical Methods

Primary analysis plan:

To test whether OH correlates with the nonmotor symptoms of fatigue, anxiety, depression, apathy, and cognitive impairment, we will compare these variables between the PD (+OH) group to the PD (-OH) group using the Mann-Whitney *U* test. Although this pilot study is likely underpowered for additional analyses, we will then construct several linear regression models with each nonmotor variable as an outcome, and also include important clinical (e.g. disease duration, total LDED) and demographic variables in the models in order to test if OH is independently associated with these nonmotor outcomes.

Secondary analysis plan:

To test whether central NA dysfunction is involved in these nonmotor symptoms, we will correlate each variable (i.e. quantified scores of depression, apathy, anxiety, fatigue, and cognition) with the difference before and after yohimbine in the change in catecholamine and AVP levels supine and at 60 degree tilt. We will also correlate the nonmotor scores with pupillary redilation speed, which measures sympathetic function, before and after yohimbine. We will compare change in anxiety, mood, and fatigue scores (measured on a visual analogue scale) before and after yohimbine between the PD (OH+) and PD (OH-) groups using the Mann-Whitney *U* test. We will also compare the changes in BP parameters before and after yohimbine between groups.

After these initial correlations and comparisons, we will construct linear regression models incorporating clinical and demographic variables of interest in order to test if our measures of NA dysfunction independently predict the nonmotor symptoms of PD, though we expect these analyses to be underpowered. Finally, we will test if central NA dysfunction (measured through changes in catecholamines and pupillary response to yohimbine, as above) explains the relationship between OH and the nonmotor symptoms of PD by incorporating our measures of central NA dysfunction into the linear regression models described above, and testing whether the relationship between OH and nonmotor symptoms persist.

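### The listed pre-yohimbine VAS comes before the first tilt, so the pre/post change spans both tilt and drug; a supine VAS after recovery and before dosing would make the tilt part visible

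*Protocol*

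**What the plan says.** Section 7.3 lists the Visit 2 steps in order. "After approximately 30 minutes of supine rest", hormone samples are drawn and the first VAS is completed ("VAS scale completion for baseline/resting anxiety, fatigue and mood"). Pupillometry follows, then the first tilt: "Tilt table to approximately 60 degrees for approximately 15 minutes; return to supine". Yohimbine is given next. A second VAS follows, described in the same resting terms and with no clock time. Then: "Patients will then be tilted to 60 degrees for a second time and remain in that position for approximately 15 minutes".

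The schedule in section 7.1 has one VAS entry before yohimbine and one after.

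Section 3.3 makes the change in these scores from before to after yohimbine a secondary endpoint. Section 8.2 gives the analysis: "We will compare change in anxiety, mood, and fatigue scores (measured on a visual analogue scale) before and after yohimbine between the PD (OH+) and" the group without OH, by Mann-Whitney U. The study has no placebo or no-drug sequence.

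Section 1.6 says that autonomic and "tilt-table testing are minimally invasive but can precipitate hypotension, bradycardia or tachycardia, palpitations, anxiety, presyncope" or syncope. Section 3.1 defines the OH group by a fall in blood pressure on standing.

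**The concern.** A change labelled as before and after yohimbine should have the drug as the main event between the two readings. Here a 15-minute tilt to 60 degrees also lies between them. By the protocol's own account tilting can provoke anxiety, which is one of the three VAS items and is also listed in section 1.6 as a possible yohimbine side effect.

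The between-group comparison does not automatically deal with this. The groups are defined by their blood pressure response to standing, and drugs such as midodrine and droxidopa are held for the visit, so an equal response to tilt cannot be taken for granted. If some tilt effect persists to the second VAS and is larger in OH patients, the analysis would read it as a stronger response to noradrenergic challenge. The plain pre/post change in section 3.3 is exposed even if the residual is the same in both groups. A larger follow-on study using the same sequence would inherit the problem, since sample size does not remove it.

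**Working it through.** **The plan's own figure.** The protocol gives no calculation for the VAS change. Its only computed figure is 4 per group (section 8.1: difference 2, SD 1, alpha 0.05, power 0.80). By the two-sided normal approximation, n = 2 × ((1.96 + 0.84)/2)² = 3.92, so 4; it reproduces. That SD is for a score rather than a pre/post change, so it does not help to size this problem.

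**Step 1: what lies between the readings.** From section 7.3: VAS 1, pupillometry, tilt 1, return to supine, yohimbine, VAS 2, tilt 2. Between VAS 1 and VAS 2 lie the tilt, the drug, and elapsed time with continued fasting and medication withdrawal.

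**Step 2: what the change measures.** For one patient,

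change = D + T + E,

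where D is the yohimbine effect, T the tilt effect still present at VAS 2, and E everything else that drifts with time. The group contrast is

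(D_OH − D_non) + (T_OH − T_non) + (E_OH − E_non).

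The tilt term vanishes only if T_OH = T_non. Nothing in the listed sequence allows T to be estimated, because no VAS follows the tilt and precedes the drug.

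**Step 3: illustration of size.** The protocol gives neither T nor the SD of the change, so the difference in residual is expressed in SDs of the change score and is assumed throughout. Inputs: 11 versus 11 (section 3.1), Mann-Whitney (section 8.2), two-sided 0.05, normal change scores, no yohimbine effect; 20,000 simulated studies per row. The last column assumes that all 22 patients share the same residual, tested with a one-sample Wilcoxon test (4,000 studies per row).

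| Residual (SD) | False group difference, if residual differs by this much | False overall change, if shared by all 22 |
|---|---|---|
| 0 | 4.6% | 4.7% |
| 0.25 | 8.4% | 20.2% |
| 0.5 | 18.6% | 57.6% |
| 0.75 | 36.2% | 90.6% |
| 1.0 | 57.3% | 98.8% |

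The table shows what a residual would do if present. It is not evidence that one exists.

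**Step 4: does a new baseline help?** With a reference reading after the tilt, the tilt term becomes T at VAS 2 minus T at the new reading. Suppose, as pure assumption, that OH patients have an excess of 20 VAS points immediately after the tilt, decaying to 5 by VAS 2:

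- pre-tilt reference (present plan): bias +5;
- reference taken immediately after the tilt: 5 − 20 = −15;
- reference taken once the excess has settled to 5: 5 − 5 = 0.

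The timing of the new reading therefore matters. Without recovery it could bias the contrast the other way and hide a real anxiety response to yohimbine.

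**The case against.** The strongest reply has four parts.

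*The text may be incomplete.* The step list refers to a Visit 2 timeline figure that is not available. It also omits items required elsewhere, such as the blood draws during the first tilt and the post-dose pupillometry. The hormone row of the schedule has one entry per period yet means two draws. This limits certainty. However, the hormone row has footnotes that say so and the VAS row has none, so the text as it stands supports one reading before and one after.

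*The after-effect may be small.* Both VAS readings are described as resting, patients return to supine, and section 1.4 puts absorption at 45 to 60 minutes. If VAS 2 is timed to absorption, tilt symptoms may have gone. Section 1.6 lists what tilting can provoke, not what persists. This stands: the size is unknown. The design as listed cannot show that it is small, though, and no time is set for VAS 2.

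*A rested pre-tilt baseline against a rested post-dose reading is a defensible like-for-like choice.* This also stands, and is a reason to keep the pre-tilt reading.

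*A reader might infer that the pupil endpoint is contaminated in the same way*, because section 6.1 says "We will repeat these studies after yohimbine administration at the time of the second HUT". The ordering is the same, but nothing in the protocol says that tilt has a lasting effect on the pupil, and that wording does not mean that patients are measured while tilted. The documents do not support a finding there.

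**Conclusion.** The point holds in limited form. On the listed sequence the pre/post-yohimbine VAS change contains any tilt after-effect, and the OH versus non-OH contrast removes it only if it is equal in both groups. An unequal residual of 0.25 to 1.0 SD would raise the false-positive rate from about 5% to between 8% and 57%. Those values are assumed, and the true residual could be near zero.

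Two stronger readings should be avoided. One is that the first tilt is known to be harder on OH patients at the time of the second VAS. That is a reasonable inference from the group definition, but the protocol does not state it or give a size. The other is that the endpoint is invalid. It is an exploratory secondary endpoint in a pilot that acknowledges limited power, and the primary comparison of Visit 1 scales is untouched. This is a cheap improvement to interpretability, not a fault in the main analysis.

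**What to change.** In section 7.3, the schedule and the Visit 2 timeline:

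- Add one supine VAS after a stated recovery period following the first tilt and before yohimbine. Define it as the pre-yohimbine reference for sections 3.3 and 8.2.
- Keep the pre-tilt VAS. Report the change from pre-tilt to post-recovery by group as the tilt effect, and repeat the yohimbine comparison with the pre-tilt baseline as a sensitivity analysis.
- State the clock time of the post-dose resting VAS, which is already listed before the second tilt.
- Optionally, repeat pupillometry at the new point and state that posture is the same for the pre- and post-dose readings. This is a precaution only.
- Record as limitations that elapsed time, fasting and medication withdrawal also lie between the readings. Without a no-drug sequence the added VAS does not control them.

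The cost is one more form and a few minutes (under 5 for pupillometry, by section 6.1), plus any recovery time beyond what is already allowed, in a visit of 4 to 6 hours. No invasive procedure is added. The new reference works fully only if the tilt effect has settled or gone by then; the reported tilt effect by group shows how much remains at that point.

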7.4 Follow-up Phone Call

24-72 hours after Visit 2 has been completed, the subjects will be contacted over the phone and will be enquired about any adverse events following research procedures.

8 Statistical Plan

8.1 Sample Size Determination

Our primary study objective is to compare the nonmotor symptoms of fatigue, anxiety, depression, apathy, and cognitive impairment between the OH and non-OH groups. If we aim to detect a clinically significant difference of 2 points on an 11 point visual analogue fatigue scale, only 4 patients in each group are needed, using a 1-way test of means and assuming a population standard deviation of 1, $\alpha = 0.05$ and $\beta=0.80$. However, it is important to recognize that this is an investigative pilot study; since little research has been done in this area and we cannot be certain

of these assumptions, it is entirely possible the study will be underpowered for at least some of our primary and secondary outcomes.

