11	STUDY MONITORING, AUDITING, AND INSPECTING	30
11.1	STUDY MONITORING PLAN	30
11.2	AUDITING AND INSPECTING	30
12	ETHICAL CONSIDERATIONS.....	30
13	STUDY FINANCES.....	31
13.1	FUNDING SOURCE	31
13.2	CONFLICT OF INTEREST.....	31
13.3	SUBJECT STIPENDS OR PAYMENTS	31
14	ATTACHMENTS	32
14.1	REFERENCES.....	31
14.2	DRUG INSERT.....	39

List of Abbreviations

OH	Orthostatic Hypotension
NA	Noradrenergic
NP	Neuropsychiatric
PD	Parkinson's disease
AR	Adrenoceptor
ED	Erectile Dysfunction
HUT	Head Up Tilt
UPDRS	Unified Parkinson's Disease Rating Scale
H&Y	Hoehn & Yahr staging
LDED	Levodopa equivalent dose
OVS	orthostatic vital signs
AVP	arginine vasopressin
NE	norepinephrine
SCOPA-AUT	Scales For Outcomes In Parkinson's Disease - Autonomic Dysfunction
TOPF	Test of Premorbid Functioning
B-SIT	Brief Smell Identification Test
GDS	Geriatric Depression Scale
GAI	Geriatric Anxiety Inventory
FSS	Fatigue Severity Scale
AES	Apathy Evaluation Scale
AD-ACL	Activation-Deactivation Checklist to assess arousal
BRIEF-A	Behavior Rating Inventory of Executive Function, Adult
NPI-Q	Neuropsychiatric Inventory Questionnaire
VAS	Visual Analogue Score
CNS	Central nervous system
ANS	Autonomic nervous system
LC	Locus coeruleus

HR	Heart rate
BP	Blood pressure
DB	Deep breathing
BMI	Body mass index
FDA	Federal Drug Administration
GMP	Good Manufacturing Practice
IND	Investigational New Drug
C-SSRS	Columbia Suicide Severity Rating Scale
CBC	Complete Blood Count
CMP	Complete Metabolic Panel

Study Summary

Title	The role of the noradrenergic system in the nonmotor symptoms of Parkinson's disease
Short Title	NA in PD
Protocol Number	Velos: D19090 D-HH IRB: 31685
IND	146199
Phase	Phase 1 – Pilot
Methodology	Cross-sectional
Study Duration	12-24 months
Study Center(s)	Single-center: Dartmouth-Hitchcock Medical Center
Objectives	To explore the association between orthostatic hypotension (OH) and the neuropsychiatric (NP) and neurocognitive nonmotor features of Parkinson's disease (PD)
Number of Subjects	22 patients total (11 patients with PD and OH (PD+OH) and 11 PD patients without OH (PD-OH))
Diagnosis and Main Inclusion Criteria	Adults patients with a diagnosis of Parkinson's Disease with and without OH

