Study Product, Dose, Route, Rationale	Yohimbine (5mg) is administered orally during Visit 2 in order to manipulate the noradrenergic system to determine the association between OH and NP symptoms in those with PD. Yohimbine is not administered as a treatment in this study, but as a pharmacologic tool to study the adrenergic system.
Statistical Methodology	In the primary analysis, between group (PD+OH and PD-OH) differences in nonmotor symptoms of fatigue, apathy, depression, anxiety, and neurocognition will be compared using nonparametric tests for ordinal variables.

1 Introduction

This document is a protocol for a human research study. This study is to be conducted according to US and international standards of Good Clinical Practice (FDA Title 21 part 312 and International Conference on Harmonization guidelines), applicable government regulations and Institutional research policies and procedures.

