3.1 General Design

This is a cross-sectional pilot study comparing 11 PD patients with OH to 11 PD patients without OH. OH will be defined as a drop in systolic BP of ≥ 20 mmHg or diastolic BP ≥ 10 mmHg within 5 minutes of standing (measured at 1, 2, and 5 minutes).^{59, 67} The study will include two clinical visits and a follow-up phone call 24-72 hours after the 2nd visit. Visits will last approximately 4-5 hours each. After consent has been signed, data from prior neurological exams, such as the H&Y staging, orthostatic vital signs (OVS) and UPDRS scores will be collected from a subject's medical record as part of study data.

For visit 1, subjects will be required to hold levodopa and other dopaminergic PD drugs on the morning of the visit, and other adrenergic medications for at least three half-lives. Subjects will bring their AM dopaminergic doses to be taken at the visit at the direction of study staff in order to coincide with the timing of procedures. Visit 1 will consist of reviewing informed consent and inclusion/exclusion criteria. The PI will confirm eligibility, (women of childbearing potential will undergo a serum pregnancy test as part of this eligibility review). Demographics, medical history, history and current use of alcohol, current and prior smoking status, and concomitant medications will be recorded. HR and BP response to deep breathing (DB) and Valsalva maneuvers, and vibrotactile detection thresholds, will also be tested. The subject will also undergo neurocognitive testing and neuropsychiatric assessments. OVS will be taken before administration of the subject's dopaminergic medications, and at approximately 30 minutes and 1 hour after dopamine administration. Dynamic pupillometry will be evaluated before and approximately 1 hour after administration of the subject's dopaminergic medications. If the subject has not had a CBC and CMP in the past 6 months, the PI will order and review these blood levels for any clinically significant abnormalities. This visit will last approximately 4-5 hours.

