3.2 Primary Study Endpoints

The primary study endpoint will be between the group (OH versus non-OH) difference in fatigue (measured with the self-reported FSS), depression (measured with the self-reported GDS), apathy (measured with the AES and NPI-Q), anxiety (measured with the GAI and NPI-Q), and cognitive impairment (measured as an average composite z-score on the neurocognitive battery).

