3.3 Secondary Study Endpoints

Secondary study endpoints will be:

- Difference between OH and non-OH group in change in supine and orthostatic catecholamine and AVP levels before and after yohimbine administration
- Difference between OH and non-OH group in change in time to pupillary redilation before and after yohimbine
- Change in self-reported anxiety, mood and fatigue before and after yohimbine
- Between group difference in baseline BP rise with yohimbine administration
- Difference in time to recovery of BP after 60 degree HUT before and after yohimbine administration
- Correlation between sympathetic function (measured with pupillary redilation and beat-to-beat BP) and levodopa use

4 Subject Selection and Withdrawal

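### Section 8.1's only sample-size calculation uses a different fatigue scale and a different test from the primary analysis, and prints power as beta

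*Protocol*

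**What the plan says.** **Planned size.** The Study Summary (Number of Subjects) gives "22 patients total (11 patients with PD and OH (PD+OH) and 11 PD patients without OH (PD-OH", and section 3.1 describes "comparing 11 PD patients with OH to 11 PD patients without OH". Neither place derives the number.

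**Calculation.** Section 8.1 begins from the primary objective and then takes a 2-point difference on an 11-point visual analogue fatigue scale. It states that "only 4 patients in each group are needed, using a 1-way test of means and assuming a population standard deviation of 1", with alpha 0.05 and beta printed as 0.80. It goes on to say that this is a pilot, that the assumptions are uncertain, and that some primary and secondary outcomes may be underpowered.

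**Primary measures.** Section 3.2 has "fatigue (measured with the self-reported FSS"), depression by the GDS, "apathy (measured with the AES and NPI-Q), anxiety (measured with the GAI and NPI-Q"), and cognition as a composite z-score. That is five domains and seven measures.

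**Primary test.** Section 8.2 names the Mann-Whitney U test. The Study Summary agrees that the symptoms "will be compared using nonparametric tests for ordinal variables".

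**Visual analogue scale.** In sections 7.2 and 7.3 it is scored from 0% to 100% and completed around yohimbine at Visit 2. It serves a secondary endpoint in section 3.3: "Change in self-reported anxiety, mood and fatigue before and after yohimbine".

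**The concern.** The calculation in 8.1 is offered for the primary objective but does not describe the primary analysis. It uses a scale that serves only a secondary endpoint here, and a test of means where ranks will be compared. No difference or SD is given for any of the seven primary measures.

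Two further statements are faulty as printed. A beta of 0.80 means 20% power. The term 1-way could mean a one-sided test or a one-way analysis of variance, and these give different answers.

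What is at stake is how a reader judges the study's sensitivity. Seeing 4 needed and 11 planned, a reader may infer a wide margin for the primary outcomes. That margin comes from an SD of 1 with no stated source, which turns 2 points into a 2-SD difference. A null result could then be read as stronger evidence than 22 patients can give.

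**Working it through.** **Inputs from section 8.1:** difference 2, SD 1 (so d = 2/1 = 2.0), alpha 0.05, and 0.80 read as power. The planned size is 11 per group (Study Summary, section 3.1) and the planned test is Mann-Whitney U (section 8.2).

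**1. Reproducing the figure of 4.** Known-SD normal formula, n per group = 2(z_alpha + z_power)²(SD/difference)²:

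- Two-sided: 2 × (1.960 + 0.8416)² × (1/2)² = 3.92, rounded up to 4.
- One-sided: 2 × (1.645 + 0.8416)² × (1/2)² = 3.09, rounded up to 4.
- Beta taken literally as 0.80 (power 0.20), two-sided: 2 × (1.960 − 0.8416)² × (1/2)² = 0.63, which would be 1 per group. So 0.80 must be power.

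With the SD estimated (noncentral t, noncentrality d√(n/2) = 2√2 = 2.83 at n = 4, 6 df):

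- One-sided t-test, n = 4: 80.2%.
- Two-sided t-test, which equals a two-group one-way analysis of variance: 65.7% at n = 4, 79.1% at 5, 87.6% at 6.

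The figure of 4 therefore holds for a known-SD formula or a one-sided t-test, but not for a one-way analysis of variance.

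**2. Same inputs, planned test.** Mann-Whitney U with exact critical values from the null distribution of U, untied normal samples, d = 2.0, and 200,000 to 400,000 simulations:

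| n per group | Two-sided rejection limit (actual size) | Power, two-sided | Power, one-sided |
|---|---|---|---|
| 4 | U ≤ 0 (0.029) | 49% | 66% |
| 5 | U ≤ 2 (0.032) | 68% | 87% |
| 6 | U ≤ 5 (0.041) | 83% | not needed |
| 11 | U ≤ 30 (0.047) | 99% | not needed |

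Four per group is too few on either sidedness. The requirement is 6 two-sided or 5 one-sided.

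**3. What 11 per group can detect.** Two-sided Mann-Whitney at 0.05, per comparison:

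| True difference | Power |
|---|---|
| 0.5 SD | 19% |
| 1.0 SD | 57% |
| 1.3 SD | 80% |
| 2.0 SD | 99% |

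The same result in points, for a 2-point difference with an assumed SD (the protocol supports no particular value): SD 1.5 gives 82%, SD 2 gives 57%, SD 2.5 gives 40% and SD 3 gives 30%.

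**4. Sensitivity to assumptions that the protocol does not state** (11 per group unless noted):

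- One-sided test: 80% at about 1.17 SD.
- Alpha 0.01 (0.05 shared over five domains): 53% at 1.3 SD; 80% at about 1.67 SD.
- Scores rounded to integers on an 11-point scale: about 77% at 1.3 SD and 54% at 1.0 SD.
- Informant measures are collected only when an informant is available; section 7.2 says "An informant (when available) will complete informant report versions of the BRIEF-A, AES", and the NPI-Q is in the same list. With informants for 8 per group, power at 1.3 SD is 65%; for 6 per group, 47%.

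**The case against.** The strongest reply is that little turns on this.

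- **Actual size.** Nobody plans 4 per group. At 11 per group the t-test has 61% power at 1.0 SD and 83% at 1.3 SD, against 57% and 80% for Mann-Whitney. The change of test costs 3 to 4 points of power, and sizing a rank test from a test of means is a common approximation. This stands: the test mismatch matters for the claim about 4 patients and hardly at all for the planned study.
- **Caveat.** The sentence is conditional, and the next one admits uncertain assumptions and possible low power for primary outcomes. This stands in part. The caveat covers the unsourced SD, but it does not say that the scale and test differ from the primary analysis, gives no figure, and leaves the beta label wrong.
- **Scale.** An 11-point scale and a 0–100% scale may be linear versions of one another, which would leave a standardised effect unchanged. That is fair. The real gap is between a visual analogue scale and the FSS, and it cannot be put in numbers because the protocol gives no FSS difference or SD.
- **Fix.** Writing two-sided and unadjusted into 8.1 could seem to set rules that the protocol has not set. In a power statement these words are the conditions under which the figure holds, not a testing rule, and the wording should make that plain.

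**Conclusion.** The concern holds and is minor. The claim that 4 patients per group suffice is wrong for the planned Mann-Whitney test on 8.1's own inputs (49% power two-sided, 66% one-sided). The calculation concerns no primary measure, and beta is misprinted. The planned 11 per group is not short for the stated effect, at 99% power for 2 SD. Its realistic sensitivity is 80% power at about 1.3 SD, which 8.1 does not convey.

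These figures assume approximately normal scores with few ties, complete data, and alpha 0.05 per comparison, two-sided unless stated. Rounded scores, missing informants or a stricter alpha all lower the power; a one-sided test raises it. Sample size, test and endpoints can stay as they are.

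**What to change.** In section 8.1, replace the sentence that arrives at 4 per group with:

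> Eleven patients per group is a pilot number. For a self-reported primary measure with complete data (e.g. the FSS), a two-sided Mann-Whitney U test at alpha = 0.05 per comparison, unadjusted for the number of domains and assuming approximately normal scores with few ties, has about 80% power for a difference of 1.3 SD, 57% for 1.0 SD and 19% for 0.5 SD. Power is lower for the informant-based NPI-Q measures if informants are missing.

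Wherever the term is kept, write power = 0.80 (beta = 0.20). Keep the existing caveat about low power.

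**Cost.** Only the wording of 8.1 changes: no added patients and no change of test or endpoint. The stated sensitivity becomes less favourable. The one example in clinical points is lost, and the protocol gives no FSS difference or SD to put in its place.
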